### **3.0 Aims**

**Aim 1 (Phase 1): Refine existing intervention components from a previous peer leader trial to allow it to be best tailored to the needs of older Black men with T2D by:**

- Conducting 10 interviews with older Black/African American men with T2D.

**Aim 2: Conduct a pilot randomized controlled trial for older Black men with T2D based on what we learn from Aim 1. Development, adaptation, and refinement will involve:**

- Developing a peer led diabetes self-management education and support intervention based on our interviews and previous research.
- Conduct an open pilot study to determine feasibility and acceptability of the peer led diabetes self-management support and estimate intervention effect size on our primary outcome of diabetes self-management behaviors and changes in A1C, as well as on secondary outcomes of change in weight, blood pressure, quality of life, diabetes related-distress, diabetes social support, and adherence to gender norms. Data from the pilot trial will help refine recruitment strategies, training materials, and protocol to be used in a larger clinical study.

**Aim 3: Conduct a qualitative process evaluation of the implementation of peer led DSMS to determine feasibility and acceptability of the intervention by:**

- Recruiting 10-12 stakeholders (facilitators, participants, peer leaders, and certified diabetes care and education specialists) and complete post intervention interviews to identify barriers, perceptions and beliefs surrounding peer led DSMS targeting older Black male populations.

**Overall impact:** Data from the pilot RCT will help refine recruitment strategies, training materials, and the study protocol to be used in a larger cluster RCT. Our study will also identify strategies to increase patient participation in intervention research and improve drop out rates. This goal is in line with the mission of NIDDK to disseminate science-based information on diabetes, to improve people's health and quality of life.

### **4.0 Participants and Recruitment**

*Participants will be 64 Black/African American men ages 55 years or older and meet the inclusion criteria listed below. During the Phase II pilot we will individually randomize each participant with a 50/50 randomization scheme to either the peer led DSMS or a control group. Four of the participants will attend 30- hours of training and function as peer leaders during the intervention DSMES.*

**Inclusion:** Inclusion criteria for the Phase II (intervention) will include males age 55 or older who are Black/African American, and who've had diagnosis of T2D for a six-month duration or longer.

**Exclusion:** Exclusion criteria for Phase II will include: non-ambulatory, serious health conditions (morbid obesity and severe symptomatic heart disease, visual impairment, renal failure, and peripheral neuropathy), psychiatric illness (severity requiring hospitalization) or cognitive deficit (illness determined using the Montreal Cognitive Assessment tool) and serious diabetes complications (e.g. blindness) that would impede meaningful participation. We considered restricting eligibility to a higher-risk population of participants with  $A1c \geq 8\%$ . Preliminary data suggest that over 50% of the proposed study sample will have an  $A1c \geq 8\%$ . Focusing on all older Black men with T2D allows us to cast a wide net for secondary prevention and public health impact. Persons who meet eligibility criteria will be invited to participate in the baseline screening assessment. While we have chosen the above eligibility criteria based on previous work, we will make adjustments to the future, larger trial, based on results and feedback from our proposed pilot.

**Participant Recruitment:** We will put up flyers describing the study. The flyers will be posted at a Detroit-based senior center (St. Patrick's), Ypsilanti Seventh Day Adventist Church, and Michigan Center for African American Aging Research Participant Resource Pool (MCUAAAR PRP) community-partners. The MCUAAAR PRP is a research volunteer registry can be accessed by scholars conducting research of Black males, 55 years of age and older who meet their study criteria. Men with T2DM identified with the help of the MCUAAAR PRP will be called by study staff and invited to participate in the intervention. [name] will also be working with the [name], the Human Subjects Assessment Core Leader. [name] will run a search in the MICHR DataDirect PHI system and identify potential participants that meet study eligibility criteria. [name] will provide the research team with the names, addresses, phone numbers, and emails of potential participants on a password protected document. Men with T2DM identified with the help of [name] will be mailed and emailed recruitment letters. Study staff will provide follow up phone calls after the letters are sent to ensure potential participants received the letter. Men interested in participating in the study will call a central office phone number or be identified on follow-up calls then they will be scheduled for screening.

**Peer Leader Participant Recruitment:** Peer leaders will be recruited from the Phase 1 Interviews, MICHR DataDirect, or identified by St. Patrick Center staff.

## **5.0 PROCEDURES**

**Screening** Individuals that are interested in participating in the study will be asked to complete a phone screen with a study team member. During the phone screen, the research staff will read a brief recruitment script and ask if the participant is interested in participating. If the individual is interested and willing, they are asked to complete a phone screen. The phone screen can be scheduled for immediately following the recruitment script or at a time convenient for the potential participant.

The phone screen will assess the following: basic demographic information and self-identified T2D diagnosis. Individuals will be eligible for a baseline interview if they meet demographic criteria (self identified as African American/black, and 55 years or older), self report having Type 2 Diabetes.

Upon completion of the phone screen, the study team member will inform the individual if they are eligible to complete the baseline interview. If the individual is eligible, a baseline assessment will be scheduled and details will be given to the individual. The purpose of this initial screen is to invite research candidates to additional eligibility screening (Baseline Assessment) having met initial criteria and for the research candidates to provide consent to answering questions at the in-person Baseline Assessment which involve Private Health Information, to be used for determining eligibility.

**Baseline Assessment** (Assessment Battery) All individuals that meet initial phone screening criteria and agree to participate will complete a baseline assessment. The physiological testing portion of the baseline assessment will be held in person at either St. Patrick Senior Center or Ypsilanti Seventh Day Adventist Church and the self-report questionnaire will be completed by the participant virtually or over the phone with a study team member. During the assessment the participant will be asked to complete questionnaires and interviews to determine if the participant is eligible to participate based on inclusion and exclusion criteria. Baseline assessments will last about two hours total. The PI will train all research staff in standardized data collection. Trained research staff will take biometric data of participants including height, weight, blood pressure, and A1c. Participant A1c values will be analyzed on site using a DCA Vantage Analyzer. All participants, including peer leader participants, will be paid \$20 for completing the assessment and the same assessments at T0 (baseline) and T1 (post-treatment).

**Randomization** Participants will be randomized to the peer leader diabetes self-management support (DSMS) group or a control group using a 50/50 randomization scheme. Participants will be aware if they are in the intervention group or the control group.

**Intervention (Peer Leader DSMS n=30)** Participants randomized to the peer led DSMS group will receive 6 100-minute weekly sessions of diabetes self-management education (DSME) delivered by a certified diabetes care and education specialists (CDCES) and co-facilitated by a peer leader (PL) delivered via the Zoom for Health a U-M service may be used for Protected Health Information (PHI, regulated by HIPPA). Next, participants will transition into 6 90-minute weekly PL led DSMS sessions

intentionally designed for older Black men with T2D. The CDCES will provide oversight to the PL and be available by phone if any clinical questions arise during the session.

**Control Group (Control n=30)** Participants randomized to the control group will receive 6 sessions of group-delivered DSME provided by a CDCES; however they will not receive any DSMS or ongoing support from PLs and the PL will not participate in the DSME sessions. Based on several years of experience in Detroit, providing all participants with DSME and educational materials minimizes ethical concerns regarding assignment of underserved populations to receive a no-treatment control. To ensure treatment fidelity, three DSMS sessions will be selected at random and recorded and rated for fidelity by our research team.

**Peer Leaders (n=4)** Participants recruited to be PLs for the intervention group will attend PL training (described below), co-facilitate DSME sessions with a CDCES, lead DSMS sessions, and complete the same battery of assessments as all other participants in the study.

**Peer Leader Training:** The peer leader training curriculum will be based on materials used by [name] and her research group. Thirty hours of training will be conducted over 6 weeks. PLs will receive training in facilitation skills, coping strategies, and empowerment-based communication skills. As noted in Phase 1, training will be adapted to include a focus on men's health issues. Training will be group-based and include both the knowledge and skills needed to implement empowerment-based DSMS. A CDCES who was involved in the development and implementation of the training curriculum in previous projects, will conduct the training. This training will support the PLs in developing communication, facilitation, and behavior change skills and opportunities to apply those skills in an experimental setting. To ensure that PLs are supported, 3-monthly meetings will be held with all PLs so that they may exchange information and support each other. As noted above, it is expected that this content will be adapted to include men's health concerns based on Phase 1. PLs will be identified from interviews, based on recommendations from the senior center, and/or from the DataDirect participant pool. PLs will be compensated at \$10/ hour for the duration of the study to defray the cost of their time and expenses.

**Follow-Ups** The follow up assessment for both the peer led DSMS group and control group will occur at three months (post-treatment assessment). All participants, including peer leader participants, will return to the St. Patrick's Senior Center or to Ypsilanti Seventh Day Adventist Church for physiological testing and complete the self-report questionnaire telephonically, or virtually. The same measurements and surveys will be completed. Participants will be compensated \$20 for completing this assessment. Data will be stored in REDCap, a secure, web-based application hosted at UM.

**Maintenance of Samples** Strategies will be used to encourage attendance of group sessions and to complete follow up interviews. Reminder emails, texts and/or calls will be sent before each session to remind participants by the study team. In addition, the study team will collect participant contact information from baseline to

follow up phase. The study team will also ask participants to provide additional contact person(s) that the study team can contact if they cannot reach the participant.

**Participant Retention** The following procedures will be used to minimize participant attrition: 1) Data collection sessions will be completed at the Senior Center site or the Ypsilanti Seventh Day Adventist Church in order to maximize the convenience of data collection for subjects, and 2) multiple techniques are used to increase the likelihood that participants will keep their data collection appointments, including advanced scheduling, multiple reminder letters, and phone reminders. Participants who withdraw will still be asked to participate in study data.

**Data Collection & Data Safety** For Phase II (intervention), data will be collected through the following methods: finger stick capillary blood samples, blood pressure measurements, weight, height, exit interviews regarding treatment satisfaction, surveys, audio recorded interviews and treatment sessions, and transcribed interviews and treatment session recordings. Data that are obtained specifically for research purposes will be collected only with informed consent. All data will be collected over the course of the award period.

At the time of study enrollment, participants will be assigned a study identification number to be used in all study materials and data for the duration of the study. All identifying information will be separated from the data and laboratory values. A master list that contains participants names and study identification number will be kept in a locked filing cabinet within a locked office in the School of Social Work at the University of Michigan. Audiotapes of treatment sessions will be stored securely on a password protected computer only accessible to study personnel and will be destroyed upon study completion. We will use DropBox, a secure platform to share these recordings, transcriptions, and other study data between study team members.

The principal investigator ([name]) and the research assistants will be the only persons who have access to the file linking study participant identification number to each subject, and this will be stored separately from study data. Participants will be assured that all data they provide to the study will be confidential to this study, unless it is necessary to “alert” the patient and possibly also their physician because of a laboratory value outside of the normal ranges that reflects a risk requiring immediate medical attention. All reports will use aggregate data. Subject names or other identifiers will not be reported. All quotes shared collected from the interviews will be de-identified for privacy. No persons from the recruitment sites will handle or have access to personal health information or participant survey data.

Data will be stored in REDCap, a secure, web-based application hosted at the University of Michigan. Analyses will be conducted using Atlas.ti. This data will be used to conduct a final refinement of treatment content as needed.

To ensure the proper monitoring of the safety of all participants and the quality of data collected, a Data Safety and Monitoring Board (DSMB) will be established that will

follow techniques suggested in the literature (Damocles, et al, 2005). The board will consist of Drs. [name], [name], and [name]. In addition, five outside members, who are not involved with the study, will serve on the DSMB **as voting members** and will be identified at a later date. Voting members will consist of University professors with experience and expertise in clinical diabetes intervention research to ensure consistency and quality of input.

## **6.0 GROUP LEADERS & TRAINING**

To ensure staff participation in data safety and monitoring activities, all members of the project team (research assistants and staff) will be trained on the specifics of the data safety and monitoring plan. Field staff will be trained on what constitutes an adverse event to a participant and instructed to report any adverse events immediately to the principal investigator, [name].

All questionnaires and instrumentations are standardized measures that have been used in our own trials and in other diabetes research and there are no significant risks anticipated related to the completion of them. However, breaks will be given as needed to reduce fatigue, or measures read to adolescents, and research assistants will be appropriately trained to obtain personal information in a sensitive fashion. Research staff will be trained in research ethics, confidentiality protection, and HIPAA prior to and throughout the study period. All CDCESs in this study are either a Registered Dietitian Nutritionist RDN) or Registered Nurse (RN) and are certified through the Certification Board for Diabetes Care and Education. The extensive CDCES certification process ensures health care professionals possess comprehensive knowledge and experience in prediabetes, diabetes prevention, and diabetes management. [name], RDN, CDCES has been working with people with diabetes for 6 years and a CDCES for 2 years. [name], RDN, CDCES has been working with people with diabetes for 28 years and a CDCES for 24 years.

The PI will monitor adverse events throughout the clinical trial period. To ensure staff participation in data safety and monitoring activities, all members of the project team (research assistants and staff) will be trained on the specifics of the data safety and monitoring plan. Field staff will be trained on what constitutes an adverse event to a participant and instructed to report any adverse events immediately to the principal investigator, [name].

The principal and co-investigators on the proposed study make up a trans-disciplinary, accomplished and collaborative team of community-based behavioral and clinical researchers. Together, our research team has a strong history of successfully implementing and publishing our work regarding diabetes interventions in high-risk communities. Most notably, Drs. [name] and [name] of the Michigan Center for Diabetes Translational Research (MCDTR), collaborated on Praise I and II, T2D randomized controlled trials of the effectiveness of church-based diabetes self-management support being conducted with Black adults in Toledo, Flint, and Metro Detroit of which [name] is PI. [name] is currently a co-investigator on Praise 2 (R01DK104733-02). Also, as part of the MCDTR, [name] is an early career trainee and [name] served as [name] primary mentor for the last 3 years. All are members of BRIDGE.

## **7.0 MEASURES**

### **Primary Outcome Measures**

Regimen adherence will be measured using the Perceived Diabetes Self-Management Scale, a self-report questionnaire used to measure a broad range of management behaviors, such as insulin management, dietary management, blood glucose monitoring, symptom response, and parent assistance/supervision.

Metabolic Control will be measured via hemoglobin A1c (HbA1c). HbA1c will be collected using the DCA 2000 point-of-care testing instrument.

### **Secondary Outcome Measures**

Adherence to gender norms will be measured using the Male Role Norms Inventory-Short Form. BMI will be calculated using height and weight. Height will be measured using a stadiometer. Weight will be measured on a high quality, calibrated digital scale. BP will be measured using a digital sphygmomanometer.

Diabetes Social Support will be measured using the Diabetes Social Support Questionnaire. Diabetes-related Distress will be measured using Diabetes Distress Scale (SF-12) and lastly, a validated Diabetes Quality of Life will be used to measure quality of life. Participants will also complete questionnaires that assess socio-demographic, behavioral, psychosocial, and health services utilization and are validated in diverse populations with diabetes.

**Specific Aim 1:** Qualitative analyses will be conducted during the development phase and on the post-intervention focus groups and interviews. First, we will develop codes utilizing a grounded theory approach and will start with the formulation of categories and definitions developed directly from the text. Content from transcripts will be coded for themes and patterns. Through this process a coding manual and definitions will be finalized. The refined manual will be used to guide ongoing coding and pairs of coders will read subsequent transcripts keeping codes that achieve 80% agreement on code application. Analyses will be conducted using Dedoose. This data will be used to conduct a final refinement of treatment content as needed.

**Specific Aim 2:** The proposed study includes a sample size of 64 Black men, 30 in the intervention arm, 30 in the control arm and 4 trained as peer leaders for the intervention arm. We will assess the impact of the intervention on diabetes management and HbA1c (primary outcomes) and on secondary outcomes using multilevel modeling, with intervention group as a between-subjects factor (2 levels) and time as a within subjects factor (3 levels). HbA1c, diabetes self-management, and social support at baseline, 3 and 6 months will be used as the dependent variables. Independent variables include intervention group, time of assessment, and interaction between time and intervention

group. Random effects will be allowed for the intercept (to allow differences in baseline measurements) and the slope (to allow differences in the trajectories of change). Covariates e.g. length of time since diabetes diagnosis, age will be tested as predictors of the outcome and retained if significant at  $p < .10$ .

**Power Analysis:** Assuming 20% attrition, we expect a final sample size of 48, approximately 12 per group (with 2 groups in the treatment arm). If we assume correlations of 0.25 between successive measurements of HbA1c, then this sample size will yield power of 0.8 to detect a difference of 0.6 standard deviation between average values of HbA1c in treatment and control groups.

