## **1.0 PHASE II RESEARCH PLAN (PILOT RANDOMIZED CONTROL TRIAL, 3 MONTHS)**

During Phase II we will be conducting a 3-month pilot randomized control trial (RCT) of virtual diabetes self-management education and support (DSMES) with peer leaders, (adapted in Phase I), to evaluate participant recruitment and retention rates, treatment and intervention satisfaction and estimate intervention effect sizes on our primary outcomes of self-management behaviors as well as on secondary outcomes such as glycemic control (HbA1c), diabetes social support, diabetes-related distress, and adherence to gender norms. This data will be collected at baseline and three months (treatment termination. Physiological data will be collected at St Patrick Senior Center or Ypsilanti Seventh Day Adventist Church and the self-report questionnaire data will be collected telephonically or virtually. Participants will be randomized to the virtual peer leader DSMES or a control group. All virtual DSMES sessions will be held on an online platform, Zoom Med. The baseline assessment and intervention period will consist of 16 weeks. In the first 2 weeks participants will complete baseline questionnaires, interviews, and physiologic testing at St. Patrick's or Ypsilanti Seventh Day Adventist Church, telephonically, or virtually. In weeks 3 to 8 participants will be simultaneously enrolled in 6 weekly virtual diabetes self-management education (DSME) classes with a certified diabetes care and education specialist (CDCES) and two peer leaders. In weeks 9 to 14 participants will be enrolled in diabetes-self management support (DSMS) sessions with two peer leaders (no CDCES). In weeks 15 and 16 of the intervention, participants will complete the post-treatment assessment battery (See Table 1). Each group will be invited to participate in the 3-month post-intervention assessment battery. Patients who do not complete the intervention phase will also be invited to participate in the 3-month assessment battery. The physiologic testing part of the assessment will be held at Ypsilanti Seventh Day Adventist Church or St. Patrick Senior Center, a non-profit that provides comprehensive services to a diverse population of more than 2,000 seniors living throughout metropolitan Detroit. Data analyses and dissemination of study findings are anticipated to be completed in months 11-12 of the study funding period. We will also be conducting qualitative interviews to better understand the acceptability and sustainability of the intervention as routine practice in a community-based clinic.

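### The Aim 2 model needs outcomes at baseline, 3 and 6 months, but the procedures schedule only baseline and a 3-month visit, and the stated power fits neither the model's contrast nor a two-visit design

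*Combined protocol and SAP*

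**What the plan says.** **Places that imply three assessments.** Section 7.0, Specific Aim 2, gives time three levels and states: "HbA1c, diabetes self-management, and social support at baseline, 3 and 6 months will be used as the dependent variables". It adds group, time and their interaction, and continues: "Random effects will be allowed for the intercept (to allow differences in baseline measurements) and the slope". The Background (Section 2.0) lists baseline, 3 months and a further 3-month follow-up, and defines the primary outcome at both later points. Section 10.0 gives mode and place for baseline, post-treatment and follow-up assessments.

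**Places that give two.** Section 1.0 says: "This data will be collected at baseline and three months (treatment termination". It places T1 at the end of a 16-week schedule: "In weeks 15 and 16 of the intervention, participants will complete the post-treatment assessment battery". The timeline table has rows for T0 and T1 only. Under Baseline Assessment in Section 5.0, payment is for "the same assessments at T0 (baseline) and T1 (post-treatment". Under Follow-Ups: "The follow up assessment for both the peer led DSMS group and control group will occur at three months (post-treatment assessment".

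**One ambiguous place.** A later sentence in Section 1.0 invites each group to a 3-month post-intervention battery. This could mean T1 or a visit three months after it.

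**Power Analysis (Section 7.0).** With 20% attrition leaving 48 men, the plan says: "this sample size will yield power of 0.8 to detect a difference of 0.6 standard deviation between average values of HbA1c". The claim is conditional on an assumed correlation of 0.25 from one HbA1c value to the next. It states neither alpha nor the number of measurements.

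**The concern.** A third visit has a mode and a place but no entry in the procedures, no payment and no timeline row. If it does not take place, part of the primary outcome defined in the Background has no data, and the Aim 2 model is specified for a time point that was never collected.

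There is a second mismatch. A difference in average HbA1c and a group-by-time interaction are different contrasts with different precision, so a power figure for one does not carry over to the other.

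This is a pilot meant to estimate effect sizes (Sections 1.0 and 3.0), so power weighs less than in a confirmatory trial. The larger cost is that the estimate carried forward to plan the next trial has no defined contrast or time point, and may be less precise than the data allow. All power figures here concern HbA1c. Sections 1.0 and 2.0 call it secondary; Section 3.0 groups it with the primary outcome, and Section 7.0 calls it primary. The plan gives no correlation or power for self-management.

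**Working it through.** **Inputs.** From the plan: 30 randomised per arm, 20% attrition, r = 0.25 between successive HbA1c values, difference 0.6 SD. Assumed: two-sided alpha 0.05, independent participants, and 24 per arm (the plan's groups of about 12, two per arm).

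**Sample size.** 60 × (1 − 0.20) = 48, or 24 per arm. This reproduces.

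**Can the model be fitted with two visits?**
- Fixed effects: 2 arms × 3 times is 6 parameters. Two visits give 2 × 2 = 4 cell means, so only 4 of the 6 can be estimated.
- Random effects: an intercept variance, a slope variance, their covariance and a residual variance make 4 parameters. Two visits supply 3 moments (two variances, one covariance), so a correlated slope is not identifiable.
- The arm effect survives: the interaction reduces to a comparison of T0-to-T1 change.
- With three visits all 6 fixed effects can be estimated and the model can be fitted.

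**Power by contrast.** Write VF for the variance of the contrast in units of the HbA1c variance. Then SE = √(2·VF/24), and power comes from the noncentral t with 46 df (45 if baseline-adjusted). For two visits, VF = 2(1 − r) = 2 × 0.75 = 1.5 for change, and 1 − r² = 1 − 0.0625 = 0.9375 for T1 adjusted for T0. Where a range is shown, the first VF assumes equal correlation between all visits and the second a correlation that decays with time, AR(1).

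| Contrast | VF | Power at 0.6 SD |
|---|---|---|
| Mean of three visits | 0.500; 0.458 | 0.82; 0.85 |
| Mean of 3 and 6 months, baseline-adjusted | 0.5625; 0.6006 | 0.77; 0.75 |
| Mean of T0 and T1 | 0.625 | 0.73 |
| T1 adjusted for T0 | 0.9375 | 0.56 |
| Three-visit averaged interaction | 1.125; 1.3125 | 0.48; 0.43 |
| Change from baseline to 6 months | 1.5; 1.875 | 0.38; 0.32 |
| T0-to-T1 change | 1.5 | 0.38 |

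The plan's 0.8 is close to the first two rows, both of which need the 6-month visit. By normal approximation the adjusted 3- and 6-month mean with equal correlation gives 0.79. No two-visit reading reaches 0.80 at two-sided 0.05.

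**Dilution.** A mean that includes baseline understates the effect, because randomisation makes the expected baseline difference zero. A 0.6 SD difference in the three-visit mean needs 0.6 × 3/2 = 0.9 SD at each later visit. If the true difference is 0.6 SD at each later visit, the three-visit mean differs by 0.4 SD and power is 0.48.

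**Difference detectable with 80% power (r = 0.25).** Two-visit change 1.01 SD; adjusted T1 0.80 SD; adjusted 3- and 6-month mean 0.62 to 0.64 SD.

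**95% confidence interval half-width, t × SE (r = 0.25).** 0.71, 0.56, and 0.44 to 0.45 SD respectively.

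**Sensitivity to r, two visits.**

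| r | Change | T1 adjusted for T0 |
|---|---|---|
| 0.25 | 0.38 | 0.56 |
| 0.5 | 0.53 | 0.65 |
| 0.7 | 0.75 | 0.81 |
| 0.9 | 0.995 | 0.997 |

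Power of 0.8 is reached at r = 0.74 for change and 0.69 for adjusted T1. The gain from adjustment is large only at low r.

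**The case against.** The schedule contradiction is hard to dispute. What can be disputed is how much follows from it.

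- **The model can largely be salvaged.** The plan does not say that the random intercept and slope are correlated. If they are independent, two visits give 3 parameters for 3 moments, which is identifiable when the T1 variance is at least the T0 variance. Time would become a two-level factor and the arm effect would still be estimated. This stands: the slope problem is confined to the correlated form. The three-level time factor still fails with two visits.
- **The power statement follows a three-level model and speaks of successive measurements.** Three visits is therefore its natural reading, and on that reading 0.8 is roughly right for an average. This also stands, but it means the figure relies on a visit that the procedures do not contain. It still does not describe the interaction, which has power 0.43 to 0.48 when averaged over the two later visits.
- **A replacement figure of 0.56 is optimistic.** It assumes independence, yet delivery is in groups. With groups of 12 and illustrative intraclass correlations of 0.01, 0.02 and 0.05 (none is given in the plan), the variance rises by 1 + 11 × ICC = 1.11, 1.22 and 1.55, and 0.56 falls to about 0.51, 0.48 and 0.39. This stands; any restated figure needs that assumption beside it.
- **It is a pilot.** This lowers the weight of the power figure, but not the need to know when the primary outcome is measured.

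**Conclusion.** The concern holds and must be fixed. The documents disagree on whether there are two or three assessments, and no section resolves it. Under the Section 5.0 schedule the follow-up part of the primary outcome has no data and the three-level model cannot be run as written; the arm comparison itself is not lost.

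The stated power of 0.8 is about right only for an average that uses the 6-month visit. It is too high for the two-visit contrasts (0.38 for change, 0.56 for adjusted T1) and for the group-by-time effect the model specifies (0.48 or less). These figures rest on two-sided alpha 0.05, independent participants, 24 per arm and the plan's r of 0.25. A higher r would raise the two-visit figures considerably, and clustering by session group would lower them. The self-contradiction in the schedule depends on none of these assumptions.

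**What to change.** Reconcile the schedule across Sections 1.0, 2.0, 5.0, 7.0 and 10.0 and the timeline table, in either direction. Name one primary contrast, and make the model and the power statement use it.

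**Option A, two visits.** Remove the 6-month time point, the three-level time factor, the random slope and the follow-up part of the primary outcome. Recommended, though not needed for validity: analyse T1 with T0 as a covariate. Restate HbA1c power as about 0.56 at 0.6 SD, or 80% power at about 0.80 SD, for r = 0.25, with a range over r and the independence assumption stated. If change is kept as the contrast, the figure is 0.38. Cost: text edits, one primary time point lost and a less favourable power figure; no new data.

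**Option B, three visits.** Add the visit to Section 5.0, the payments and the timeline. Treat time as categorical, preferably with a common baseline mean. Name 3 months, 6 months or their average as the contrast. For the baseline-adjusted average the power statement barely changes (80% power at 0.62 to 0.64 SD); for a single visit it does (0.53 to 0.56 at 0.6 SD if baseline-adjusted). Cost: another round of on-site A1c testing, more exposure to attrition, and 64 × $20 = $1,280 if the payment is kept. On timing, weeks 15–16 plus 13 is weeks 28–29 from the start of baseline. If months 11–12 are kept clear for analysis, 10 months is about 43.5 weeks, and 43.5 − 29 = 14.5, so baseline would have to start by about week 14 of the award. The planned start dates cannot be read from the timeline as supplied, so this needs checking against it.

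**Either way,** state alpha and the number of measurements, and give a correlation for self-management as well as HbA1c.
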